STIMULANT OXYTOCIN STUDY

NCT03016598

[figure not shown]
12/18/2017

Study Protocol

RESEARCH DESIGN

We conducted a randomized, double-blind, placebo-controlled study to examine the effects of oxytocin administration on stimulant use, psychosocial treatment engagement, and stress-reactivity in a sample of 40 individuals with stimulant use disorder receiving opioid agonist therapy within an opioid treatment program at the San Francisco and Oakland VA. Following successful screening and an initial baseline visit, participants were randomized to receive either oxytocin 40 IU or placebo intranasally twice daily for six weeks.

FIGURE 1

Research Participants:

We enrolled 40 male research participants with active stimulant use disorder and stabilized on opioid agonist therapy in an opioid treatment program (OTP). OTP clinics operate under strict state and federal guidelines for treatment structure and monitoring. Each patient receiving opioid agonist therapy from the OTP who is actively using stimulants is in “Phase 0” within the OTPs at the San Francisco and Oakland VA. Phase 0 patients must report to the clinic every day the clinic is open for observed opioid agonist dosing (i.e., no take-home doses), must submit urine for random toxicology screening approximately once every two weeks, and are required to attend weekly psychoeducation/therapy groups within the clinic. All patients in the OTP are assigned an individual counselor who meets with them at least monthly to support the lifestyle changes necessary to progress in recovery. Phase 0 patients typically meet with their counselors more frequently.

Recruitment: Participants were recruited from the OTP through the use of flyers posted visibly in clinic common areas and referrals from clinic counselors who were made familiar with inclusion/exclusion criteria through presentations at staff meetings and “Dear Provider” letters.

Adherence Monitoring: Study staff trained in proper spray application (Guastella, Hickie, et al. 2013) intranasally administered participants’ morning study drug doses. Each participant was given a nasal spray bottle and trained in proper spray application by study staff. Participants were to administer their evening dose 8-10 hours following their morning dose. Each week, participants will be incentivized to bring their nasal spray bottle from the previous week, whether full or empty, for adherence monitoring via weighing. We successfully used similar contingent management strategies in our previous study of

repeated oxytocin administration in patients with co-occurring cocaine and opioid use disorders. Our participants brought their nasal spray devices in for weighing 98% of the time (no participant forgot more than once) and collectively self-administered >78% of their evening doses.

Randomization: Participants were randomized 1:1 to receive either oxytocin or placebo. A randomization plan was created using www.randomization.com. Randomization was managed by the Investigational Drug Pharmacist at the San Francisco VA, who also managed the double blind.

Inclusion Criteria: Participants must be at least 18 years old, enrolled as a patient at the San Francisco or Oakland VA OTP, be on a stable dose of methadone or buprenorphine for at least two consecutive weeks, and have at least one documented routine urine toxicology screen positive for cocaine or methamphetamine in the past month.

Exclusion Criteria: Urine toxicology screen positive for heroin in the past month; meeting *Diagnostic and Statistical Manual of Mental Disorders, 5th Edition* (DSM-V) criteria for previous or current psychotic disorder, severe neuropsychological disorder, premenstrual dysphoric disorder, or current moderate severe alcohol use disorder; active suicidal or homicidal ideation; hemodialysis; sensitivity to E 216, E 218, and chlorbutanol hemihydrate (preservatives used in nasal spray); using hormone supplementation; positive urine pregnancy test or women of child-bearing age not practicing an effective means of non-hormonal birth control; or nasal obstruction, discharge, or bleeding.

METHODS

All measures are listed in detail below. In sum, our primary outcome measure will be **(1)** Stimulant positive urine drug screen collected at baseline and weekly throughout the study. To assess psychosocial measures, participants and their clinic assigned counselor will complete **(2a)** the Working Alliance Inventory – Short Revised (WAI-SR) (Hatcher & Gillaspy 2006), client and therapist forms, respectively, at baseline and after six weeks as well as **(2b)** OTP attendance rates. Additionally, in response to a Trier Social Stress Test, we will measure, **(3a)** self-reported stimulant craving by completing the Cocaine Craving Questionnaire (CCQ-Brief) modified to include methamphetamine in addition to cocaine, **(3b)** psychophysiological measures, including heart rate and heart rate variability, **(3c)** stress biomarker measurements, including salivary cortisol and DHEA, and **(3d)** self-reported anxiety.

See **Figure 1** for Study Design Outline.

PROCEDURES

Screening/Baseline: Potential participants were screened by study staff on site and, if preliminarily eligible, signed a brief clinic-specific consent in order for us to confirm eligibility via OTP medical records. Eligible participants were invited for a baseline interview, which included: 1) written informed consent, 2) a medical history and brief physical exam conducted by a study physician, 3) a structured mental health interview conducted by an advanced psychology trainee, 4) baseline measurements, and 5) a urine pregnancy test (for female participants).

Daily: We asked participants to report daily on their illicit drug use from the previous 24-hours, including specific drug, amount, and route of administration. We also monitored daily OTP clinic attendance.

Weekly: Participants provide a weekly urine sample, which was analyzed for various drugs of abuse.

MEASURES

[figure not shown]
Screening Measures:

- 1) **Structured Clinical Interview for DSM-5 Disorders – Clinical Trials Version (SCID-5-CT):** a structured psychiatric interview based on current diagnostic standards, customized to the inclusion and exclusion criteria of our clinical trial.

Outcome Measures:

- 1) **Stimulant positive urine drug screen:** (Jufer, Wstadik et al. 2000, Preston, Epstein et al. 2002) was measured from baseline and weekly urine samples. Urine samples were screened for a variety of drugs of abuse.
- 2) a. **Working Alliance Inventory – Short Revised (WAI-SR):** (Hatcher & Gillaspy, 2006): is a well-validated 12-item measure of therapeutic alliance. Participants completed individual “client forms” for their clinic-assigned individual counselor at baseline and after six weeks. Likewise, the counselor completed the “therapist form” for each participant at baseline and after six weeks of study participation. Time required for administration per form: <5 minutes.
b. **Attendance in OTP clinic:** Daily attendance at OTP clinic was tracked for each participant.

FIGURE 2

Psychophysiology measurements
Baseline CCQ-Brief, salivary biomarkers, Likert scales
Figure 6: Social Stress-Induced Cocaine Craving Paradigm. TSST = Trier Social Stress Test, CCQ-Brief –Cocaine Craving Questionnaire-Brief, salivary biomarkers = cortisol and dehydroepiandrosterone, Likert scales = subjective stress and anxiety.

- 3) **Trier Social Stress Test (TSST) (see Figure 2):** in order to evaluate response to social stress, participants engaged in the TSST paradigm at study baseline and after six weeks of intranasal oxytocin or placebo. The TSST is a standardized and well-validated psychological stress challenge which has shown utility for evoking a strong cardiovascular and HPA axis stress response (including salivary cortisol) in a laboratory setting (Dickerson & Kemeny 2004). After a 5-minute preparation period, participants are instructed to give a speech and perform serial subtractions, for five minutes each, in front of a panel of stone-faced adjudicators.
 - a. **Cocaine Craving Questionnaire-Brief (CCQ-Brief):** (Sussner, Smelson et al. 2006) is a valid and reliable 10-item self-report instrument, with each item scored on a scale 1-7, used to measure the respondent's general cocaine craving. We amended this to also include methamphetamine and asked for participants' stimulant of choice. Participants

completed the amended CCQ-Brief at baseline, immediately after the TSST, and 20 minutes after the TSST.

- b. **Psychophysiological Stress Measures:** consisted of two main outcome variables: *heart rate* and *heart rate variability*. We recorded continuous physiology during the TSST, we will include the 5-min averages for: baseline, speech prep, speech, mental arithmetic, and 15-20 mins post-TSST.
- c. **Salivary cortisol and dehydroepiandrosterone (DHEA):** are biological markers of HPA-axis stress reactivity. We will collect salivary cortisol and DHEA at baseline, immediately after the TSST, and 20 minutes after the TSST.
- d. **State-Trait Anxiety Inventory, 6-item version (STAI-6):** participants will rate their levels subjective anxiety using the STAI-6 at baseline, immediately after the TSST, and 20 minutes after the TSST.

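### Do the entry criteria need a stimulant use disorder diagnosis because the protocol describes its sample by that disorder?

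*Protocol*

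**What the plan says.** The protocol names the population by diagnosis twice. Research Design describes the study as carried out "in a sample of 40 individuals with stimulant use disorder receiving opioid agonist therapy", and Research Participants says that those enrolled were male "research participants with active stimulant use disorder".

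The Inclusion Criteria set four conditions: adult age, enrolment in one of the two OTP clinics, a stable methadone or buprenorphine dose, and a urine result. On the last, a participant must "have at least one documented routine urine toxicology screen positive for cocaine or methamphetamine in the past month". Stimulant use disorder is not named there. Research Participants says that Phase 0 patients, meaning those actively using stimulants, "must submit urine for random toxicology screening approximately once every two weeks".

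The Exclusion Criteria use DSM diagnoses for several conditions, among them "or current moderate severe alcohol use disorder". They deal with heroin by urine result alone.

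Screening/Baseline says that candidates signed a short consent "in order for us to confirm eligibility via OTP medical records". Those who passed were invited to a baseline visit that included a structured mental health interview. Screening Measures identifies an interview, the SCID-5-CT, as "customized to the inclusion and exclusion criteria of our clinical trial".

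**The concern.** A trial's result applies to the people its entry rules admit. Here the description uses a diagnosis and the rule uses a laboratory result. One positive screen documents use on one occasion. A patient who uses stimulants occasionally, without meeting DSM-5 criteria, could satisfy all four inclusion conditions. Phase 0 status does not close the gap, because it too is defined by use.

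Two features sharpen the worry. The authors wrote a DSM term for alcohol in the same section, so they knew how to specify a substance diagnosis. And the check of clinic records comes before the structured interview, which could suggest that eligibility was already settled when the interview took place.

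At stake would be the reach of the conclusion: a statement about stimulant use disorder might rest partly on people without it. If such people responded differently, the average effect would also differ from the effect in those with the disorder.

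**Working it through.** The plan states no figure that depends on this point, so there is none to reproduce. The check is mainly a reading of the text.

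**1. Criteria against description.** None of the four inclusion conditions names the disorder, and no sentence makes the diagnosis a condition of entry. The gap in the wording is confirmed.

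**2. Was the record check the last eligibility step?** It cannot have been. The exclusions cover psychiatric diagnoses, suicidal ideation, pregnancy and nasal obstruction. These correspond to the interview, the physical examination and the pregnancy test, all of which take place at the baseline visit. Research Design places randomization after screening and that visit. The interview therefore stood between the record check and randomization and could act as a gate. The documents also do not say what the clinic records held; they may have included diagnoses.

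**3. What the interview was for.** It was tailored to the inclusion as well as the exclusion criteria. Age, clinic enrolment, dose stability and a urine result need no psychiatric interview. The mention of inclusion criteria has clear content if a stimulant diagnosis was being checked. It may equally be a stock phrase, so this supports the reading without proving it.

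**4. Is alcohol a fair contrast?** Only in part. Heroin is handled by urine toxicology with no DSM term, just as stimulants are. The criteria use urine results for those drugs and a diagnosis for alcohol. They do not single out the condition under study for looser treatment.

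**5. How loose is the urine rule?** One screen about every two weeks gives about two a month, so one positive in two is enough. If the two screens are independent (assumed) and each is positive with probability p (assumed), the chance of qualifying in a given month is 1 − (1 − p)²:

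- p = 0.10: 1 − 0.81 = 0.19
- p = 0.25: 1 − 0.5625 = 0.44
- p = 0.50: 1 − 0.25 = 0.75

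This describes frequency of use. It says nothing about how many of those who qualify lack the diagnosis, so it does not measure the gap.

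**6. Dilution.** Let q be the share with the disorder, d the effect in them and e the effect in the others. The average effect is q·d + (1 − q)·e. The documents give neither q nor e. For illustration, take 36, 32 or 28 of the 40 as diagnosed (assumed), so q = 0.90, 0.80 or 0.70. If e = 0, the average is 90%, 80% or 70% of d. If e = d, there is no dilution. Nothing in the documents chooses between these cases.

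**7. Effect on the analysis.** Eligibility is fixed before allocation and is the same for both arms, so it cannot bias the comparison. The mixed model for Aim 1 in the SAP's Data Analysis section uses weekly urine results and no diagnosis variable. Limiting it to diagnosed participants would widen standard errors by roughly √(40/n): 1.05, 1.12 or 1.20 for n = 36, 32 or 28 (same assumed counts; simple scaling that ignores the repeated measures). It would not correct any bias, because there is none.

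**The case for a change.** The strongest case for acting is that a description is not an operational criterion. Two sentences saying that participants had the disorder do not tell a reader how that was established, and the section that should say so is silent. The interview text names no stimulant module and no threshold. The remedy would be cheap: a count by arm of those who met the diagnosis or, if it was never recorded, a change in how the population is described.

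Most of this stands. The documents do not show that the diagnosis was required, and it would be wrong to infer that it was. But the argument shows missing detail, not a defective design. It gives no reason to think that undiagnosed people entered, and the protocol says the opposite. Adding a criterion serves no purpose if enrolment is over, and Research Participants reports the 40 as already enrolled (other parts of the protocol mix past and future tense). The count by arm and the choice of population wording belong to the trial report.

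The urine rule also has its own logic. It selects on the measure that serves as the primary outcome, so those who enter have had a recent positive result that can change during treatment.

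**Conclusion.** No change to the plan follows. The inclusion list is shorter than the population description, and the text does not say how the two were joined. That is a gap in detail which the authors can fill from their own screening records when they report. If the SCID-5-CT recorded the diagnosis, the baseline table can show it by arm. If it did not, the accurate description is OTP patients on opioid agonist therapy with a recent stimulant-positive screen, a broader group than those with the diagnosis.

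The randomized comparison is unaffected, and no stated sample size or analysis changes. The size of any dilution is unknown; the 90%, 80% and 70% figures rest on assumed counts and on assuming no effect in the undiagnosed.

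This conclusion relies on the protocol's statement that the 40 enrolled had the disorder, and on enrolment being complete. Figure 1 of the protocol and the part of the SAP before Data Analysis were not available for this check, and either might describe screening more fully.

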#### Data Analysis:

Aim 1: We will employ linear mixed effects models to examine within- and between-group variability in positive stimulant urine drug screens across 6 weeks.

Aim 2: We will employ linear mixed effects models to examine within- and between-group differences in (H2) client and therapist WAI ratings and (H5) attendance rates.

Aim 3: We will use linear mixed effects models to assess within- and between-group differences in the following stress measures related to the Trier Social Stress Test (conducted at baseline and post-6 weeks): (H3) Psychophysiological measures (HR, HRV), (H4) self-reported stimulant craving, (H6) salivary stress biomarkers (cortisol and DHEA), and (H7) self-reported anxiety (STAI-6).

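### Does the plan need an analysis of the daily drug-use reports, given that Aim 1 models only the weekly urine screen?

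*Protocol*

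**What the plan says.** The Protocol's Research Design section says the trial is to "examine the effects of oxytocin administration on stimulant use, psychosocial treatment engagement, and stress-reactivity". The primary outcome in Methods is "Stimulant positive urine drug screen collected at baseline and weekly throughout the study", and the outcome entry repeats that it "was measured from baseline and weekly urine samples".

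The daily reports appear under Procedures, Daily: "We asked participants to report daily on their illicit drug use from the previous 24-hours, including specific drug, amount, and route of administration". Methods says "All measures are listed in detail below". The outcomes that follow are the urine screen, the working alliance inventory, clinic attendance, craving, heart rate and its variability, cortisol and DHEA, and anxiety. Self-reported drug use is not among them.

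In the SAP's Data Analysis section, Aim 1 reads: "We will employ linear mixed effects models to examine within- and between-group variability in positive stimulant urine drug screens across 6 weeks". Aim 2 covers "within- and between-group differences in (H2) client and therapist WAI ratings and (H5) attendance rates", and Aim 3 covers the stress-test measures.

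Part of the SAP was not available for this review. The available text labels hypotheses H2 to H7 without defining them in full.

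**The concern.** The objective is stimulant use, not abstinence alone. A positive or negative screen shows whether there was any use inside the detection window, so a participant who goes from five use days a week to four may stay positive every week. The trial collects daily data that bear on frequency, yet no available outcome or aim takes them up. Daily attendance, tracked under the same Procedures heading, does become an outcome and is analysed under Aim 2.

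At stake would be a null screen result that could not be told apart from less frequent use without stopping. Any later analysis of the reports would be open to a charge of selection, because drug, amount, route and summary could all be chosen after seeing results.

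A smaller worry is that the available text does not say how missed urine screens are handled.

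**Working it through.** There is no planned figure to reproduce. The documents give 40 participants, 1:1 allocation and six weeks, but no use frequency, detection window, reporting accuracy or missing-data rate. All of these are assumptions below.

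**1. Hand calculation.** With d use days a week, independent days and a detection window of w days, P(positive) = 1 − (1 − d/7)^w. For w = 3:

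| Use days | P(positive) | Fall in days | Fall in positivity | Relative fall, days | Relative fall, positivity |
|---|---|---|---|---|---|
| 5 to 4 | 335/343 to 316/343 | 1/7 = 14.3 points | 19/343 = 5.5 points | 20% | 19/335 = 5.7% |
| 4 to 3 | 316/343 to 279/343 | 14.3 points | 37/343 = 10.8 points | 25% | 37/316 = 11.7% |
| 3 to 2 | 279/343 to 218/343 | 14.3 points | 61/343 = 17.8 points | 33% | 61/279 = 21.9% |
| 2 to 1 | 218/343 to 127/343 | 14.3 points | 91/343 = 26.5 points | 50% | 91/218 = 41.7% |

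On the relative scale the screen always falls by less than use days do. In percentage points, the scale on which a linear model of positive screens estimates the arm difference, it falls by less at high use and by more at three days or fewer.

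**2. With variation between people** (normal person effect on the logit scale, SD 1.0 to 2.0; w = 2 to 4), the same fall of one day a week lowers positivity by:

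- 5 to 4 days: 5.7 to 12.2 points
- 4 to 3 days: 10.0 to 14.3 points
- 3 to 2 days: 15.9 to 17.3 points
- 2 to 1 days: 18.7 to 24.6 points

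At 5 days, about 61 to 88% of participants would be positive on all six screens. At 2 days the figure is 7 to 28%.

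**3. Where the population sits.** Eligibility asks for one positive routine screen in the past month, and routine screens come about every two weeks. One positive out of roughly two is enough, so infrequent users qualify and the high-use case cannot be taken as typical.

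**4. Simulated power**, 20 per arm, t-test on person means at two-sided 0.05. Reports are missing on 30% of use days and 10% of other days. Mean candour (the share of use days admitted) is 70%, with between-person SD 0, 0.20 or 0.32. Repeat runs differ by up to about 0.03.

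| Use days | Screen | Reports, SD 0 | SD 0.20 | SD 0.32 |
|---|---|---|---|---|
| 5 to 4 | 0.19–0.38 | 0.29–0.51 | 0.24–0.35 | 0.19–0.26 |
| 5 to 3 | 0.65–0.91 | 0.80–0.98 | 0.70–0.90 | 0.57–0.73 |
| 3 to 2 | 0.27–0.48 | 0.29–0.51 | 0.27–0.44 | 0.21–0.32 |
| 2 to 1 | 0.41–0.72 | 0.40–0.72 | 0.38–0.66 | 0.33–0.55 |

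The reports do clearly better only at high use with fairly uniform candour. At lower use they give little or no gain, and mostly do worse once candour varies.

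**5. Cost of adding a self-report outcome.** Aim 2 tests whether treatment changes the alliance with the counsellor, so candour might differ by arm. At 70% against 80%, with no true effect, the false difference is 0.45 to 0.49 reported days a week and the rejection rate is 0.10 to 0.23. A table of agreement with urine by arm would flag this only 10 to 13% of the time.

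**6. Missed screens.** Take 80% true positivity and suppose every missed week is in fact positive. At 2% against 10% missing, the available screens show 0.78/0.98 = 79.6% and 0.70/0.90 = 77.8%, a bias of 1.8 points. At 1% against 3% it is 0.79/0.99 − 0.77/0.97 = 0.4 points. Counting missed screens as positive has its own bias if missingness is unrelated to use: (0.10 − 0.02) × (1 − 0.80) = 1.6 points and (0.03 − 0.01) × 0.20 = 0.4 points. Neither handling is clearly better. Missing screens should be few, because "Phase 0 patients must report to the clinic every day the clinic is open for observed opioid agonist dosing" and staff give the morning study dose.

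**The case for a change.** The strongest case for a change is that the data are already collected, that naming one supportive summary such as stimulant-use days out of reported days needs only SAP wording, and that doing so in advance removes the freedom to choose among summaries later. In a population using about five days a week the screen loses much of a modest reduction, and most participants would be positive at every visit.

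The high-use arithmetic stands, and so does the point about selection: an analysis of the reports devised after unblinding would have to be labelled post hoc. What does not stand is the step from there to a defect. The high-use case is one assumption among several that the eligibility criteria allow. The gain would be mainly descriptive, and the added outcome is unverified and exposed to a bias that the available check would rarely detect. There is also a practical limit. Reports cover the previous 24 hours, so if they are taken at clinic visits (the text does not say), some days around closures would have no report. The Protocol describes the trial largely in the past tense, so a prespecified addition may no longer be possible.

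**Conclusion.** No change to the plan. The observation is accurate for the available text: the daily reports are a study procedure that no available outcome or aim takes up. It is not an error. The Protocol lists its outcomes separately from its procedures, the primary outcome is objective, and the Aim 1 analysis matches it. Nothing stated would give a wrong result. Because part of the SAP was not available, the reports may be covered there, and the absence cannot be charged to the plan as a whole.

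In percentage points, the screen under-registers a fall of one use day a week at about five days (5.7 to 12.2 against 14.3 points) and falls by more than use days do at about three days or fewer (15.9 to 24.6 against 14.3). Its relative fall is smaller throughout. The reports offer no dependable gain in power, and differential candour could produce false rejection rates of 0.10 to 0.23. These figures rest on assumed use frequency, detection window, between-person spread, candour and missingness, none of which the documents give. Without a named analysis, analysts would sensibly treat the reports as descriptive. The missed-screen rule is a small gap, worth about 0.4 to 1.8 points in the cases shown, and the obvious remedy has a bias of similar size.

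### No pre-randomisation attendance period or baseline adjustment is specified for OTP attendance (2b/H5), so change from before treatment cannot be estimated and the arm comparison loses precision

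*Protocol*

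**What the plan says.** - Protocol, Outcome Measures, 2b: "Daily attendance at OTP clinic was tracked for each participant". No start date, window or rate definition is given.
- Protocol, Procedures, Daily: "We also monitored daily OTP clinic attendance". This follows the Screening/Baseline paragraph and again has no start date.
- Protocol, Procedures, Screening/Baseline: the visit includes "3) a structured mental health interview conducted by an advanced psychology trainee, 4) baseline measurements". Those measurements are not itemised, so attendance is neither named nor excluded. Before that visit, participants "signed a brief clinic-specific consent in order for us to confirm eligibility via OTP medical records".
- SAP, Data Analysis, Aim 2: linear mixed models are to examine "within- and between-group differences in (H2) client and therapist WAI ratings and (H5) attendance rates". No baseline term, time unit or denominator for attendance appears.
- For the other outcomes, the protocol places the urine screen at baseline and weekly, and both the WAI-SR and the TSST at baseline and six weeks.

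**The concern.** Psychosocial treatment engagement is one of the trial's stated objectives, and attendance is one of its two outcomes, with its own hypothesis (H5).

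If the attendance series begins with treatment, every within-group contrast starts from a treated week. By then, staff-given morning doses and the bottle-return incentive are also in place. An effect present from the first week would not show as change.

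Between arms, participants may differ in how regularly they came to clinic before the trial. With about 20 per arm, a chance imbalance in this could be neither seen nor adjusted for, and the spread it creates stays in the error of the arm difference. A random intercept in the mixed model does not remove that spread from the arm main effect. It only accounts for it.

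**Working it through.** **Inputs from the documents.** The trial has 40 participants ("in a sample of 40 individuals with stimulant use disorder"). Allocation is even ("Participants were randomized 1:1 to receive either oxytocin or placebo"), so 20 per arm is assumed. Treatment lasts six weeks ("participants were randomized to receive either oxytocin 40 IU or placebo intranasally twice daily for six weeks"). The available text gives no alpha, power, effect size, attendance rate, SD or correlation for attendance, so there is no figure of the plan's own to reproduce. Everything below is an illustration under stated assumptions.

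**1. How much of the noise is usual attendance?** Assume weekly rates with a constant within-person correlation ρ and weekly SD of 1. The variance of a six-week mean is (1 + 5ρ)/6, of which ρ is stable between-person difference.
- ρ = 0.2: 0.2/0.333 = 60%
- ρ = 0.4: 0.4/0.5 = 80%
- ρ = 0.6: 0.6/0.667 = 90%
- ρ = 0.8: 0.8/0.833 = 96%

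A pre-randomisation mean over k weeks has variance (1 + (k−1)ρ)/k, and its correlation r with the six-week mean is ρ divided by the square root of the product of the two variances. For ρ = 0.4 and k = 4, r = 0.4/√(0.5 × 0.55) = 0.76, which leaves 1 − 0.76² = 42% of the variance. For ρ from 0.2 to 0.8, two weeks of history remove about 20% to 85% of the variance, and four weeks about 30% to 90%.

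**2. Detectable difference in SD units (two-sided 0.05, 80% power).** Unadjusted: √(2/20) × (1.960 + 0.842) = 0.886 SD. Adjusted: multiply by √(1 − r²).

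| r | Detectable difference (SD) |
|---|---|
| none | 0.886 |
| 0.3 | 0.845 |
| 0.5 | 0.767 |
| 0.7 | 0.633 |
| 0.9 | 0.386 |

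**3. In attendance points.** Simulation assumptions: logit-normal attendance propensity (mean 1.7, SD 1.0 on the logit scale, so mean attendance a little over 80%), 24 open days before randomisation and 36 on study, 20 per arm, and covariate adjustment against the raw difference. The unadjusted standard error is about 4.9 points, which implies an SD of 4.9/√(2/20) = 15.5 points for the 36-day rate.

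| Observed pre/on correlation | Simulated SE | 4.9 × √(1 − r²) |
|---|---|---|
| 0.23 | 4.8 | 4.8 |
| 0.38 | 4.6 | 4.5 |
| 0.54 | 4.2 | 4.1 |
| 0.72 | 3.5 | 3.4 |

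The simulated values sit slightly above the formula, as expected when the slope is estimated from 40 people. Type I error stays near 5%.

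For a true rise of about 10 points, simulated power goes from about 0.72 to 0.77, 0.84 and 0.94 in the last three rows. These power figures are flattering. The SE under no effect would give 10/4.9 = 2.04 and a power of about 0.53; the higher values arise because a rise towards 100% narrows the spread in the treated arm. The change in standard error is the safer summary.

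**4. Near a ceiling.** With mean attendance of about 93%, the standard error falls from about 2.5 to 2.4, 2.3 and about 2.0 for latent correlations of 0.5, 0.7 and 0.9. A 10-point rise is then impossible, since 93 + 10 exceeds 100.

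**5. What on-study data alone can show.** A slope over weeks 1 to 6 has per-person variance (1 − ρ)/17.5, and usual attendance cancels from it. The detectable arm difference in change over the five intervals is 5 × 0.886 × √((1 − ρ)/17.5): 0.95 weekly SD at ρ = 0.2 and 0.47 at ρ = 0.8. So a within-group trend and an arm-by-week contrast can be estimated, but both start from treated week 1.

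**The case against.** The strongest reply is that the documents are silent here, and silence is not a defect. A reader might infer that attendance was tracked only after the trial was running. The text does not say so: no start date is given and the baseline measurements are not itemised. Figure 1 (the design outline) and part of the SAP were not available, and either could define an attendance baseline. That stands, and it limits the point to what the available text specifies.

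A reader might also infer that the within-group analysis has no starting point at all. That goes too far. The SAP does not promise change from before treatment, and a mixed model on weekly rates can estimate a trend across weeks 1 to 6. Only the pre-treatment reference is missing.

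Nor is the between-arm comparison biased. Randomisation protects it, and the cost is precision on a non-primary outcome.

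The size of the gain is also open to challenge. Nothing in the documents shows that attendance is a stable personal habit. At an observed correlation near 0.2 the gain is negligible (4.9 to 4.8 points). Daily attendance is compulsory for these patients, so rates may be near a ceiling. Study dosing and incentives could weaken the link between earlier and on-study attendance.

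Finally, the consent to consult OTP records is described for eligibility only, and the documents do not describe what attendance data those records hold. These reservations also stand. They reduce the expected benefit but do not remove the case for a cheap covariate.

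**Conclusion.** The point holds in limited form. The available text specifies neither a pre-randomisation attendance period nor a baseline adjustment for H5, although the other outcomes named above have a baseline and the SAP plans a within-group difference. If only on-study data are used, change from before treatment cannot be estimated, and the unbiased arm comparison is noisier than it need be.

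Adjustment lowered the standard error in every setting tested, from almost nothing at low correlation to about 30% at high correlation ((4.9 − 3.5)/4.9 = 29%). This rests on 20 per arm and on assumed attendance rates and correlations that the documents do not supply. It is a worthwhile improvement to a non-primary outcome and does not threaten the trial's validity.

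**What to change.** 1. Check Figure 1 and the remainder of the SAP for an attendance baseline. If one exists, cite it in Aim 2.
2. If not, confirm that consent or ethics approval covers using OTP records for outcome data.
3. If so, extract attended and clinic-open days for a fixed window before randomisation: 4 weeks, or since OTP entry if shorter. Define the rate as days attended divided by clinic-open days, the same way before and during treatment.
4. State in Aim 2 that the deciding H5 estimate is the oxytocin-versus-placebo difference in on-treatment attendance, adjusted for the pre-randomisation rate. Report within-group change from that window as descriptive only.

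The cost is a one-time record extraction for 40 people, one covariate, a few lines of SAP text and possibly a consent or ethics notification, which may be harder to arrange if participation has ended. Recent OTP entrants will have shorter, noisier windows. If the records cannot be used, say so, and describe the within-group result as a trend across treated weeks.
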